6.3.2.4 Subgroup Analyses

Only descriptive summaries will be provided for the primary endpoint for each subgroup. See Section 4.3 for list of subgroups of interest.

6.3.3 Secondary Efficacy Endpoints

If the main analysis of the primary endpoint is significant, then the main analyses of the key secondary endpoints are tested using the Hochberg procedure, as described in Section 5.2. The key secondary endpoints include: CGI-I; MSA-QoL motor subscale; MSA-QoL non-motor subscale; UMSARS Part I and Part II Total Score.

6.3.3.1 S01: Clinical Global Impression of Improvement (CGI-I)

The CGI-I scale is a clinician-rated scale measuring the change in the subject's total improvement from the time of study start. It is scored on a 7- point scale, ranging from 1 (very much improved) to 7 (very much worse), with a score of 4 indicating no change. The CGI-I should be assessed relative to the CGI-S at the Week 0 (Day 1) visit as the reference. The CGI-I will be administered at Weeks 4, 12, 24, 36 and 48 and/or early discontinuation.

The estimand for this endpoint will pursue a hypothetical strategy of estimating the effect of Verdiperstat relative to placebo had all subjects stayed on treatment. Intercurrent events will be handled by only using the on-treatment data.

The number and percentage of subjects in each category will be summarized: very much improved, much improved, minimally improved, no change, minimally worse, much worse, and very much worse. A similar summary table will be generated for CGI-I with combined categories: 1-3 (improved), 4 (no change), 5-7 (worse).

In addition, the CGI-I scores will be transformed into numeric values ranging from 1 to 7 (1 indicating "very much improved" and 7 indicating "very much worse"). Descriptive statistics for the CGI-I score will be presented by visit.

The transformed CGI-I score at Week 48 will be analyzed similar to the MMRM methodology described in Section 6.3.1, but with baseline CGI-S score as the covariate. If found to be statistically significant, similar methods detailed in Section 6.3.2.3 will be employed.

6.3.3.2 S02: MSA-Quality of Life (MSA-QoL) Motor Subscale

The MSA-QoL is a subject-rated scale that was designed to measure health-related quality of life specifically in subjects with MSA. It assesses activities of daily living and has subscales for motor, non-motor, and emotional/social domains. The MSA-QoL will be administered at Baseline, Weeks 24, 48, Baseline-Extension, Week 12-Extension, Week 24-Extension, Week 36-Extension, Week 48-Extension, and/or early discontinuation.

Change from baseline in the motor subscale score of the MSA-QoL at Week 48 will be analyzed with the MMRM methodology described in Section 6.3.1. If found to be statistically significant, the same methods detailed in Section 6.3.2.3 will be employed.

Descriptive statistics for the MSA-QoL motor subscale score and the change from baseline in the subscale score will be presented by treatment group and visit as described in Section 6.3.1.

6.3.3.3 S03: MSA-Quality of Life (MSA-QoL) Non-Motor Subscale

The MSA-QoL is described in Section 6.3.3.2.

Change from baseline in the non-motor subscale score of the MSA-QoL at Week 48 will be analyzed with the MMRM methodology described in Section 6.3.1. If found to be statistically significant, the same methods detailed in Section 6.3.2.3 will be employed.

Descriptive statistics for the MSA-QoL non-motor subscale score and the change from baseline in the subscale score will be presented by treatment group and visit as described in Section 6.3.1.

6.3.3.4 S04: UMSARS Part I and Part II Total Score

As described in Section 6.3.2.1, the UMSARS is a clinician-rated scale comprised of four parts. The Part I (Historical Review) and Part II (Motor Examination) total score will be assessed as a secondary endpoint.

Change from baseline in the UMSARS Part I and Part II total score at Week 48 will be analyzed with the MMRM methodology described in Section 6.3.1. If found to be statistically significant, the same methods detailed in Section 6.3.2.3 will be employed. The UMSARS Part I and Part II total score will exclude item 11 from Part I (sexual function).

Descriptive statistics for the UMSARS Part I and Part II total score and the change from baseline total score will also be presented by treatment group and visit as described in Section 6.3.1.

6.3.3.5 S05: Patient Global Impression of Severity (PGI-S)

The PGI-S is a patient-rated scale and will be administered at Baseline and Weeks 4, 12, 24, 36 and 48 and/or early discontinuation. The patient will rate how they perceive the severity of their illness. The PGI-S is a 1-item questionnaire on a 4-point scale scored as: "normal" (1), "mild" (2), "moderate" (3), or "severe" (4).

Change from baseline in the PGI-S score at Week 48 will be analyzed with the MMRM methodology described in Section 6.3.1.

Descriptive statistics for the PGI-S score and the change from baseline score will be presented by treatment group and visit as described in Section 6.3.1.

Frequency table for PGI-S score shift from baseline to any post-baseline score will be presented as well.

6.3.3.6 S06: Clinical Global Impression of Severity (CGI-S)

The CGI-S scale is a clinician-rated scale measuring the severity of the subject's illness. It is scored on a 7- point scale ranging from 1 (normal, not ill at all) to 7 (among the most extremely ill patients). The CGI-S will be administered at Baseline and Weeks 4, 12, 24, 36 and 48 and/or early discontinuation.

The change from baseline in the CGI-S score will also be analyzed using a MMRM analysis model, similar to the analysis described in Section 6.3.1.

The number and percentage of subjects in each category will be summarized: normal, not at all ill; borderline ill; mildly ill; moderately ill; markedly ill; severely ill; and among the most extremely ill patients.

In addition, the CGI-S scores will be transformed into numeric values ranging from 1 to 7 (1 indicating "normal, not at all ill" and 7 indicating "among the most extremely ill patients"). Descriptive statistics for the CGI-S score and the change from baseline will be presented by treatment group and visit as described in Section 6.3.1.

Frequency table for CGI-S score shift from baseline to any post-baseline score will be presented as well.

6.3.3.7 S07: UMSARS Part III

As described in Section 6.3.2.1, the UMSARS is a clinician-rated scale comprised of four parts. The Part III (Autonomic Examination) score includes supine and standing vital signs, orthostatic change, and orthostatic symptoms and will be assessed as a secondary endpoint.

Change from baseline in the UMSARS Part III results (orthostatic change in systolic BP, diastolic BP, and heart rate) at Week 48 will be analyzed with the MMRM methodology described in Section 6.3.1.

Descriptive statistics for orthostatic change in systolic BP, diastolic BP, and heart rate and the change from baseline for each of these parameters will also be presented by treatment group and visit as described in Section 6.3.1. In addition, the number and percentage of subjects with orthostatic symptoms will be presented by treatment group and visit.

[figure not shown]
6.3.3.8 S08: UMSARS Part IV

[figure not shown]
As described in Section 6.3.2.1, the UMSARS is a clinician-rated scale comprised of four parts. The Part IV (Global Disability Scale) score will be assessed as a secondary endpoint.

[figure not shown]
Change from baseline in the UMSARS Part IV score at Week 48 will be analyzed with the MMRM methodology described in Section 6.3.1.

Descriptive statistics for the UMSARS Part IV score and the change from baseline score will also be presented by treatment group and visit as described in Section 6.3.1.

[figure not shown]

6.4 Safety

Safety and other analyses will be conducted on treated subjects by treatment group. For the DB Phase outputs, treated subjects in the DB Phase will be used; for the OLE Phase outputs, treated subjects in the OLE Phase will be used; and for the combined phase outputs, DB and OLE Verdiperstat treated subjects will be used. All safety and other data will be listed for the entire study with screening, DB Phase, and OLE Phase data presented together.

Safety outcome measures include extent of exposure, compliance to study treatment, AEs, laboratory assessments, vital signs, ECGs, concomitant medications, and the S-STS questionnaire.

6.4.1 Adverse Events

AEs will be coded using MedDRA and displayed in tables and listings by system organ class (SOC) and preferred term (PT), unless specified otherwise.

Analyses of AEs will be performed for those events that are considered treatment-emergent AEs (TEAEs), where treatment-emergent is defined as any AE that developed, worsened, or became serious on or after first dose of study drug and prior to 30 days after the last dose of study drug.

A TEAE overview without SOC and PT will be presented as the number and percentage of subjects with any of the following TEAEs: TEAE leading to death; serious TEAE; serious TEAE related to study drug; TEAE leading to study drug discontinuation; any TEAE; TEAE related to study drug; and severe AE.

In addition, TEAEs will be tabulated by SOC and PT for all treated subjects for the following endpoints for the DB and OLE phases, separately and combined:

- TEAEs
- TEAEs related to treatment (includes, possibly related and related)
- TEAEs by highest severity (mild, moderate, severe)

- TEAEs related to treatment by highest severity
- Treatment-emergent SAEs
- TEAEs leading to discontinuation of study treatment

In the above tabulations, each subject will contribute only once (i.e., the most related occurrence or the most severe occurrence) to each of the incidence rates in the descriptive analysis, regardless of the number of episodes.

The TEAEs summary by SOC and PT will also include the number of unique AE occurrences; unique occurrences mean that if a subject had an AE twice, both will be reported (i.e., the subject will contribute twice to the count of events).

All AEs occurring pre-treatment and during the entire study will be listed. Additional listings will be provided including deaths, SAEs, AEs leading to discontinuation of study drug, and events of special interest (see Section 6.4.2).

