2 STUDY DESCRIPTION

2.1 Study Design

Verdiperstat is a Phase 3, multicenter, randomized, double-blind, 2-arm placebo-controlled parallel-group study designed to evaluate the efficacy and safety of Verdiperstat in a population of patients with MSA (MSA-C and MSA-P). The study is planned to consist of a Screening phase lasting a maximum of approximately 6 weeks and a randomized double-blind treatment phase of approximately 48 weeks, per Figure 1. It is anticipated that the Randomization phase will include a dose titration period of approximately 2 weeks followed by a full dose period of approximately 46 weeks. Approximately 325 subjects in total are planned to be randomized in a 1:1 ratio to receive either Verdiperstat 600 mg BID, or matching placebo BID. It is anticipated that subjects will be assessed at clinic visits, per the Schedule of Assessments & Events (Appendix I: Schedule of Assessments and Events – Randomized Double-blind Phase). In addition, subjects who are completing or have completed Week 48 of the double-blind treatment phase may be offered the opportunity to enroll in an OLE phase, in which subjects will receive open-label treatment with Verdiperstat for approximately 48 weeks (Appendix II: Schedule of Assessments and Events – Open-Label Extension Phase).

Figure 1: Study Schematic

Screening Phase

The purpose of the Screening phase is to ensure that the appropriate subjects are entered into the trial and remain stable during the pre-treatment period. It is estimated that approximately 360 subjects will enter the Screening phase of the trial. The Investigator will determine that the subject meets eligibility criteria and will collect demographic and medical data presenting a full characterization of the subject. All attempts should be made to obtain medical and pharmacy records to confirm the subject's medical and medication treatment history. During Screening,

Biohaven (or designee) may review relevant clinical information to confirm the diagnosis and subtype of MSA, for study eligibility and stratification prior to randomization. Screening will range from a minimum of 1 day to a maximum of 42 days.

If initial Screening lab sample results do not meet protocol-specified eligibility criteria and the Investigator determines that a repeat sample may meet the range required for eligibility, a repeat lab sample may be collected (one repeat collection/analysis allowed).

Rescreening

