Full dose period: Starting with Week 3 and for the remainder of the study, subjects will ingest either 600 mg BID of Verdiperstat or matching placebo BID. Subjects should take the study drug twice a day; dosing in the mornings and evenings approximately 12 hours apart.

At Weeks 4, 12, 24, 36 and 48, the morning dose of study medication should not be taken on the day of the study visit until it is administered by site personnel during the study visit, so that one pre-dose (trough) and one post-dose pharmacokinetic (PK) sample can be collected approximately 2-4 hours post-dose. Study medication can be taken without regard to meals, however, the last meal time prior to collection of PK samples should be obtained. If subjects have difficulty tolerating Verdiperstat 600 mg BID, then the dose may be adjusted.

End of Treatment

Patients will have a Week 48/Early Discontinuation visit when they either complete the study at Week 48 or discontinue from study medication early (prior to Week 48). The Week 48/Early Discontinuation assessments/procedures should be conducted as an in person visit at the study site. Every effort should be made to conduct the Week 48 visit and maintain a +/- 7 day window. However, due to the COVID-19 public health emergency, the Week 48 visit window may be expanded beyond the +/- 7 day window up to an additional 12 weeks (maximum treatment duration of 60 weeks). However, every attempt should be made to conduct the visit as close as possible to the date that the visit is due. Under these circumstances, the Investigator should discuss the specific circumstances of these cases with the sponsor medical monitor (or designee), who must approve the request to extend the treatment duration, prior to any modification of the visit window.

If the Week 48 visit window is modified, participants should have safety assessments evaluated remotely and safety labs conducted at the time of the scheduled Week 48 visit.

For subjects who discontinue early, depending on the reason for early discontinuation, some procedures may not be conducted at this visit. Conduct of all procedures, if possible, is encouraged. If possible, the subjects who discontinue from study medication prior to Week 48 should be contacted by a follow up phone call at the approximate time of their Week 48 visit, to collect information on clinical status (including Time to Event measures of disease progression, and if applicable, AEs, SAES).

Open-Label Extension Phase

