The OLE Phase is an optional 48 week open-label treatment phase following the double-blind phase of the study. All subjects who enter the OLE phase will sign a new informed consent form.

All participants must have their Week 48 visit in-person prior to enrolling in the OLE phase. Due to COVID-19, the timing of this visit may be delayed.

Participants who early-terminated from the double-blind phase of the trial or who discontinued the study medication for any reason will not be eligible for enrollment in the OLE phase.

When a site is open for recruitment to the OLE Phase, participants completing the double-blind treatment phase who choose to participate in the OLE phase and are eligible to continue, must consent to the OLE phase and directly enter the OLE phase starting at Week 48 visit of the double-blind treatment phase. The Week 48 visit will serve as the Baseline-Extension visit in the OLE phase for participants who move directly from the double-blind treatment phase to the

OLE. Thereafter, participants will undergo visits at Week 2-Extension, Week 4-Extension, Week 8-Extension, Week 12-Extension, and then every 12 weeks of the OLE phase as outlined in Appendix II: Schedule of Assessments and Events – Open-Label Extension Phase.

A participant who has completed the double-blind treatment phase of the study prior to the OLE phase of the study being approved and open for recruitment at the study center where they are participating, can reconsent and start the OLE phase as long as the investigator determines that open-label treatment offers an acceptable risk-benefit profile for the participant. Once the study site is open for recruitment for the OLE, study participants who previously completed the double-blind phase of the study will have up to approximately 12 weeks (from the date of OLE opening at the site) to enroll and complete the OLE Baseline-Extension Visit, regardless of their date of double-blind phase completion.

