6.1.1.1 Tables

Unless otherwise specified, the DB Phase and OLE Phase will be analyzed separately. For tables summarizing subjects who received at least one dose of DB or OLE study medication (Verdiperstat), summary statistics will be calculated from both phases combined for subjects randomized to Verdiperstat and from the OL Extension Phase for subjects randomized to placebo.

Treatment Group Presentation

Tables present results by treatment group (i.e., Verdiperstat and placebo) with the following exceptions:

- Results for the enrolled analysis set are presented only by overall, without treatment group.
- Results for study population parameters (see Section 6.2) and pre-treatment safety also include overall.

• OLE tabulations will include the sequence of the treatment, i.e., Verdiperstat/ Verdiperstat or Placebo/ Verdiperstat.

Time-to-event Tables

Time-to-event endpoints are summarized with KM tables displaying the following at each time interval:

- Number of subjects at risk, defined as those who did not have the event just prior to the start of the interval and who were not censored prior to the interval
- Number of subjects with events, defined as those who had the event for the first time during the interval
- Number of subjects censored, defined as those who did not have the event and whose censoring date/time (e.g., last contact date, last available measurement date/time) is in the interval
- Cumulative probability of having the event with lower and upper 95% CI limits, based on the KM product limit method.

Time-to-event distributions of endpoints are tabulated with the following descriptive statistics: number and percentage of subjects with events; number and percentage of subjects censored in or before the last time interval; number and percentage of subjects censored in the last time interval; time-to-event median, first quartile, and third quartile, with 95% CI. The 95% CI for the median is estimated using the method of Brookmeyer and Crowley.

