The number and percentage of subjects who had dose titrations during the OLE phase will also be summarized by time point and dose.

Double-Blind and Open-Label Extension Phases Combined

For the combined phase data, the extent of subject exposure (i.e., treatment duration) to Verdiperstat during the entire study will be quantified as the number of days on study medication (Verdiperstat) and measured from the time the subject received the first dose of Verdiperstat until the time the subject received the last dose of Verdiperstat, either at the end of the study or withdrawal from the double-blind or OLE phases. Treatment Duration includes missed dose days within a study phase and excludes the dosing break between study phases (i.e., (last dose day of Verdiperstat study medication – first dose date of Verdiperstat study medication + 1) – (number of days with a dosing break between the double-blind and OLE phases)).

The extent of subject exposure (i.e., total days on Verdiperstat) during the entire study will also be calculated to exclude days when subjects missed a dose (i.e., Treatment Duration – number of days a subject missed all doses of study medication).

Additionally, percent (%) compliance will be calculated as (total days on Verdiperstat study medication) / (Treatment Duration of Verdiperstat study medication) × 100.

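### The combined double-blind plus extension TEAE tables give crude frequencies over unequal exposure, so they reflect time observed as well as risk; person-time rates should be added

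*SAP*

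**What the plan says.** SAP 6.4.1 plans system organ class and preferred term tables in three versions: "TEAEs will be tabulated by SOC and PT for all treated subjects for the following endpoints for the DB and OLE phases, separately and combined". Section 6.4 sets who is in the third version: "for the combined phase outputs, DB and OLE Verdiperstat treated subjects will be used". Section 6.1.1.1 sets which time they contribute: "summary statistics will be calculated from both phases combined for subjects randomized to Verdiperstat and from the OL Extension Phase for subjects randomized to placebo".

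The phases have equal planned length. SAP 2.1 describes a "randomized double-blind treatment phase of approximately 48 weeks" and an extension in which "subjects will receive open-label treatment with Verdiperstat for approximately 48 weeks". The extension is optional and selective: "Participants who early-terminated from the double-blind phase of the trial or who discontinued the study medication for any reason will not be eligible". Under the COVID-19 provision the double-blind phase can run longer, to a "maximum treatment duration of 60 weeks".

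For the statistic itself, 6.4.1 gives numbers and percentages of subjects in the overview. In the class and term tables it counts each subject once, and the main TEAE table adds a count of occurrences. The section calls the per-subject figures incidence rates but defines no person-time. Elsewhere, 6.2.6.1 says that "the extent of subject exposure (i.e., treatment duration) to Verdiperstat during the entire study will be quantified", with the break between phases removed. The visible text does not link that quantity to the adverse event tables.

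**The concern.** A crude percentage of subjects ever having an event depends on how long they were watched. In the combined tables that time differs by design between the two sequences, and further with extension entry, dropout and visit delays. If the tables are laid out by sequence, the columns have unequal exposure. If they are pooled, the mixture sits inside one percentage. The SAP does not fix the layout, but the problem arises either way.

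This trial is exposed to the problem for two reasons. Protocol 8.1.3 allows medically significant signs and symptoms of the disease to be reported as adverse events, and in a progressive disease these can accumulate with follow-up whatever the drug does. Protocol 1.4 reports rises in mean TSH over time on drug, and 8.1.8 makes thyroid function an event of special interest. A reader will want to know whether later thyroid events reflect a higher rate or longer observation, and an ever/never percentage does not separate the two. What is at stake is the reading of the all-verdiperstat safety summary.

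**Working it through.** **The plan's own figure.** The documents give no figure for the TEAE tables. The sample size supplies the arm size and dropout used below. The difference is 0.40 × 4.88 = 1.952 with SD 4.85, so n per arm = 2 × (1.960 + 1.282)² × (4.85/1.952)² = 129.7, rounded up to 130, or 260 in total. Then 260/0.80 = 325. Both stated figures reproduce.

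**Inputs from the documents.** 48 weeks per phase; 325/2, taken as 162 per arm; about 20% dropout, so 80% completing.

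**Assumptions, not in the documents.** Constant hazard, identical on drug and placebo; 48-week risk p of 5%, 20% or 50%; a share e of completers entering the extension, from 50% to 100%.

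**Step 1: the maximum contrast.** Risk over 96 weeks = 1 − (1 − p)².

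| Risk at 48 weeks | Risk at 96 weeks | Ratio |
|---|---|---|
| 5% | 1 − 0.95² = 9.75% | 1.95 |
| 20% | 1 − 0.80² = 36% | 1.80 |
| 50% | 1 − 0.50² = 75% | 1.50 |

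Adding the 30-day tail of the TEAE window to both sides lowers these ratios to 1.87, 1.73 and 1.44.

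**Step 2: partial extension entry.** Entrants per arm: o = 0.8 × 162 × e, which is 64.8 at e = 0.5 and 129.6 at e = 1. Non-entrants count as 48 weeks.

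- Verdiperstat-randomized column: [(162 − o)p + o(1 − (1 − p)²)]/162.
- Placebo-to-verdiperstat column: p.
- Pooled: [(162 − o)p + o(1 − (1 − p)²) + o·p]/(162 + o).

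Worked case, p = 20%, e = 1: (32.4 × 0.20 + 129.6 × 0.36 + 129.6 × 0.20)/291.6 = 79.06/291.6 = 27.1%.

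| Risk at 48 weeks | Verdiperstat-randomized, e = 0.5 to 1 | Placebo-to-verdiperstat | Pooled, e = 0.5 to 1 |
|---|---|---|---|
| 5% | 6.9–8.8% | 5% | 6.4–7.1% |
| 20% | 26.4–32.8% | 20% | 24.6–27.1% |
| 50% | 60–70% | 50% | 57.1–61.1% |

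Mean exposure in the pooled set is (97.2 × 48 + 64.8 × 96 + 64.8 × 48)/226.8 = 61.7 weeks at e = 0.5. At e = 1 it is (32.4 × 48 + 129.6 × 96 + 129.6 × 48)/291.6 = 69.3 weeks.

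**Step 3: the crediting of dropouts.** Step 2 gives every dropout a full 48 weeks and every entrant a complete extension. As a further assumption, let the 20% double-blind dropouts average 24 weeks, and let 20% of extension entrants leave after 24 weeks. At p = 20% the risks are 1 − 0.8^0.5 = 10.6% at 24 weeks and 1 − 0.8^1.5 = 28.4% at 72 weeks. With e = 1:

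- A 48-week phase with such dropout: 0.8 × 20% + 0.2 × 10.6% = 18.1%. This applies to the placebo-to-verdiperstat column and to double-blind placebo.
- Verdiperstat-randomized: (32.4 × 10.6% + 103.7 × 36% + 25.9 × 28.4%)/162 = 29.7%.
- Pooled: (162 × 29.7% + 129.6 × 18.1%)/291.6 = 24.5%.

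So the level falls from 27.1% to about 24.5%. The ratio to a 48-week column is nearly unchanged: 24.5/18.1 = 1.35 against 27.1/20 = 1.36.

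**Step 4: the same data as a rate.** First events per 100 person-years = −ln(1 − p)/48 × 52.18 × 100, which is 5.6, 24.3 and 75.3 for p of 5%, 20% and 50%. Under the constant hazard it is the same in both sequences and at every entry rate.

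**The case against.** The strongest answer is that the comparison that matters is already protected. The primary safety objective is safety relative to placebo, and the double-blind tables answer it by arm with equal planned follow-up. Protocol 9.4.7 and SAP 6.4.1 require the phases to be shown separately. SAP 6.1.1.1 shows the extension by treatment sequence, again over equal planned time. The combined tables have no placebo column, and no passage plans to set them against double-blind placebo. All of this stands. A reader might infer that the primary safety conclusion is biased, but the documents do not support that: the defect is confined to a supplementary descriptive set.

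Several narrower objections also stand.

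- A reader might infer that the SAP contains no exposure adjustment at all. The file cannot show that: the text of SAP 6.4.2 is not in the public copy, Protocol 9.4.4 is redacted, and table templates are in a separate document. The statement holds only for the visible text of 6.4.1.
- A reader might take 96 against 48 weeks as typical. It is the maximum, because entry is optional and early discontinuers are excluded.
- A reader might conclude that the percentages track time and not risk. They track both, and events confined to early dosing would hardly move.
- Occurrence counts are planned alongside percentages, so a crude event rate could be worked out from planned outputs. The visible text does not commit to displaying one, and counts without person-time have the same weakness.

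Finally, a rate would still not be a fair comparison with double-blind placebo, since extension entrants are selected completers at a later stage of disease. That limits what the fix can do, but it does not make the crude percentage a better summary.

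**Conclusion.** The point holds for the combined-phase TEAE tables only. As written, their crude percentages and counts rise with follow-up at an unchanged event rate. Under a constant hazard and no drug effect, the two sequences can differ by up to 1.5- to 1.95-fold for 48-week risks of 50% down to 5%. The pooled percentage is about 1.1 to 1.4 times the 48-week value when 80% complete and 50–100% of completers enter the extension (57.1/50 to 7.1/5). The pooled levels are upper-end for the reasons in step 3. The extended window works the other way for any subjects who use it. The event risks and entry rates are assumptions, since the documents give none.

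No test, randomized comparison or primary endpoint changes. It is a worthwhile, inexpensive improvement that prevents a foreseeable misreading of the all-verdiperstat summary.

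**What to change.** In SAP 6.4.1, add to each combined-phase TEAE table the person-years at risk and first events per 100 person-years. Show double-blind rates by arm on the same scale. Keep the crude percentages, the occurrence counts and the phase-specific tables. Extension-only tables do not need the change on this ground, because planned follow-up is equal there.

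Define time at risk as first verdiperstat dose to first event or the end of the TEAE window, built on the 6.2.6.1 exposure. The definitions need aligning first. Section 6.2.6.1 stops at the last dose and removes the whole break between phases. The TEAE window runs until 30 days after the last dose, and SAP 7.1 applies its exclusion of the break only where it exceeds 30 days. Events and person-time should follow one rule.

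The cost is SAP wording and a few table columns; the underlying exposure is already derived and trial conduct does not change. The downside is that a constant-rate summary can hide early clustering and does not remove confounding from disease progression or selective extension entry. A table footnote should say so.
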